Molecular profile of vaginal wall tissues (all clinical sites). High quality RNA from tissue samples obtained in this trial will facilitate a comparative analysis of gene expression related to matrix synthesis and degradation. It is not possible to analyze hundreds of genes involved in these pathways especially in ~392 (196 ea of muscularis and mucosa) tissues. We, therefore, choose to quantify mRNA levels of select genes related to matrix synthesis and degradation to determine a molecular profile of estrogen action in vaginal tissues.

Analysis of tissues from women enrolled in our pilot trial indicated that, of 7 genes important in collagen and elastin synthesis, the magnitude of estrogen-induced change was greatest and most consistent in *Col1a1* (6-fold). With increased numbers of subjects, we expect that vaginal estrogen will also result in increased *LOX* gene expression (which correlates with enzyme activity) in the vaginal muscularis. Hence, we will utilize qPCR to measure relative levels of *LOX* and *Col1a1* mRNA as markers of collagen synthesis in all tissue samples from this trial. *Col3* and *tropoelastin* will be used as potential negative controls and at least two housekeeping genes will be used as normalizers (*h36B4* and *GAPDH*).

Our pilot trial indicated that mRNA levels for serine protease and MMP inhibitors were not regulated by vaginal estrogen. The single exception was the serine protease inhibitor, *α 1-antitrypsin*, which tended to be increased in mucosal samples from women treated with estrogen ($P=0.27$). In contrast with protease inhibitors, 2 protease genes (*MMP1* and *MMP12*), were significantly decreased in tissues from CE-treated women, and MMP9 activity was also downregulated dramatically in CE-treated women. Thus, *MMP1*, *MMP12*, and *α 1-antitrypsin* will be quantified in all tissue samples using *MMP2* and *TIMP1* as negative controls.

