Aim 3 Outcomes: If there is 10% loss of patients from randomization (baseline) to surgery, there will still be 100 patients per arm eligible for the standardized intraoperative apical anterior vaginal wall surgical biopsy. Our pilot trial (Section 2.2a, *Humans*) indicates sufficient power to determine 2-fold differences in collagen subtypes and MMP activity using tissues from UTSW. Further, with ~42 samples from UTSW (21 in each group), this will provide 80% power to also detect 2-fold differences in LOX protein and mRNA expression. All Aim 3 outcomes of interest (e.g. histological wall thicknesses, qPCR-determined relative mRNA levels, collagen subtypes and elastic fiber content, collagenase and protease activity) will be summarized using the following statistics: mean, standard deviation, median, minimum and maximum. Additionally, because most biomarkers are not normally distributed, the geometric mean and standard deviation based on natural log transformed values will also be calculated. Summaries will be constructed by treatment group (CE vs. placebo) and comparisons conducted using 2-tailed Student’s *t*-tests comparing natural log transformed levels. Because this translational study (Aim 3) is considered to be descriptive and a relatively large number of markers are being considered, all p-values will be presented without adjustment for multiple comparisons and should be interpreted accordingly. We will correlate any treatment-group differences in vaginal wall or smooth muscle histomorphology, ERs, collagen gene expression, and protease downregulation with *clinical outcomes*, namely, objective or subjective “success” as outlined in Aims 1 and 2.

Ideally, CE cream application will support an improvement in prolapse recurrence success/failure rates 1y postop, but even if CE cream has a null or non-significant effect, the entire population will be divided into prolapse repair failures (*cases*) and successes (*controls*), and, controlling for CE cream exposure, univariate comparisons will be made of the continuous outcomes from Aim 3 (2-tailed Student’s *t*-tests). Those variables that attain a significance level of 0.1 or less in univariate analyses will be considered jointly in a multivariable backward stepwise logistic regression model. An accepted “rule of thumb”

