is that one needs 10 events (i.e. 10 cases of prolapse repair failure) for each predictor added to the model (i.e., for each degree of freedom).^{108,109} If a total of 67 cases are identified (i.e., 40% repair failure in 222 participants and 25% patient loss), this would be sufficient to analyze up to at least 7 variables in the multivariable model. Thus, we will identify important biomarkers that predict greater risk for failure of native tissue repair. These findings could theoretically be used to tailor the choice of surgical approaches for these higher-risk patients.

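### The Aim 3 failure-biomarker model counts the ten-failure rule only on markers that reach the model, states no exit level or validation, and so cannot support the claim that predictors will be identified

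*Combined protocol and SAP*

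**What the plan says.** Section 9.5, under Aim 3 Outcomes, divides the whole trial population into repair failures and successes. It then states that, "controlling for CE cream exposure, univariate comparisons will be made of the continuous outcomes from Aim 3", by two-tailed t-tests. The selection rule follows: "Those variables that attain a significance level of 0.1 or less in univariate analyses will be considered jointly", and this is done "in a multivariable backward stepwise logistic regression model". No significance level for staying in the model is given.

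The size of the model is justified by a rule of thumb requiring "10 events (i.e. 10 cases of prolapse repair failure) for each predictor added to the model". The event count is conditional: "If a total of 67 cases are identified (i.e., 40% repair failure in 222 participants and 25% patient loss". From this the plan infers room for at least seven variables and concludes that "we will identify important biomarkers that predict greater risk for failure of native tissue repair". It adds that the findings could theoretically help to tailor the choice of surgery.

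Earlier in the same section, Aim 3 is called descriptive, with the remark that "a relatively large number of markers are being considered, all p-values will be presented without adjustment for multiple comparisons". Section 9.4.2 lists the markers and plans the all-site molecular profile in about "392 (196 ea of muscularis and mucosa) tissues".

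**The concern.** Every marker compared between failures and successes has a chance to be selected, so the information in the failures is used up by all candidates and not only by those that survive the screen. A rule of ten failures per predictor protects a model whose variables were fixed beforehand. Counted after a P≤0.1 screen on the same data, it gives little protection. Screening followed by backward elimination also favours markers whose effects happen to be overestimated in this sample, so the retained coefficients are biased away from zero and the model fits better than it would in new patients.

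The plan has no step that would reveal this: no limit on candidates, no shrinkage, no resampling, no validation set. The event count is nevertheless the stated ground for saying that predictors of failure will be identified. At stake is whether a reader can trust any marker reported from this analysis.

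**Working it through.** **1. The plan's own figure.** 0.40 × 222 × 0.75 = 66.6, which rounds to 67, so the stated count reproduces. Then 67/10 = 6.7, or six full degrees of freedom. Seven at ten failures each would need 70. Estrogen exposure is to be controlled for and takes one degree of freedom, which leaves five markers.

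**2. Number of candidates.** The documents give no total. The all-site profile in section 9.4.2 names 12 genes: Col1a1, LOX, Col3, tropoelastin, MMP1, MMP12, α1-antitrypsin, MMP2, TIMP1, ERα, ERβ and VEGF. In two tissue layers that is 12 × 2 = 24. The histology list adds eight measures: three thicknesses, elastic fibre, collagen, CD68, actin and smooth muscle myosin. That gives 24 + 8 = 32. A narrower reading drops the four genes used as negative controls (Col3, tropoelastin, MMP2, TIMP1), leaving eight. Eight genes in two layers, or eight genes in one layer plus eight histology measures, gives 16. Protein and enzyme measures, available only from about 42 primary-site participants, are left out of both counts. With them, the section lists about 58 distinct measures before layers are counted.

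**3. Failures per candidate.** 67/32 = 2.1; 67/16 = 4.2. Ten per candidate would need 320 or 160 failures.

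**4. Closed form, 32 independent markers unrelated to failure.**
- Expected to pass the screen: 32 × 0.10 = 3.2.
- At least one passes: 1 − 0.90^32 = 97%.
- At least one has P below 0.05: 1 − 0.95^32 = 81%.

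**5. Simulation of the whole procedure.** Inputs: 167 participants (222 × 0.75 = 166.5), 67 failures and 100 successes; normal markers with equal pairwise correlation and no relation to failure; t-test screen at P≤0.10; backward logistic elimination with estrogen exposure forced in. The number of candidates, the correlation and the exit level are assumptions, because the plan states none of them. The table shows the approximate percentage of trials whose final model keeps at least one marker.

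| Candidates | Exit level | Correlation 0 | 0.3 | 0.6 |
|---|---|---|---|---|
| 16 | 0.05 | 58 | 51 | 31 |
| 24 | 0.05 | 72 | 61 | 36 |
| 24 | 0.10 | 92 | 82 | 61 |
| 32 | 0.05 | 82 | 69 | 43 |
| 32 | 0.10 | 95 | 90 | 64 |

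Repeat runs differ by up to about three points. The results for 16 candidates at exit 0.10 lie inside this range. With 32 independent markers and exit 0.05, about 1.7 markers are kept on average.

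**6. Apparent performance.** Among models that keep a marker, the mean AUC in the data used for fitting is about 0.61 to 0.66, although the true value is 0.50.

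**7. Fewer failures.** Section 9.2 sizes the trial on 65% versus 80% success, an average failure rate of (35% + 20%)/2 = 27.5%. That gives 222 × 0.75 × 0.275 = 46 failures and four full degrees of freedom. The selection rates hardly move: for 32 independent markers at exit 0.05, 81% to 83%.

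**The case against.** The plan calls Aim 3 descriptive, admits that many markers are tested and tells the reader to interpret unadjusted P values accordingly. That covers the estrogen-versus-placebo comparisons it accompanies. It does not deal with bias from data-driven selection, and the text then moves from description to a claim of identification.

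Other objections stand and limit the point:

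- A reader might infer that the procedure will usually produce false predictors. The documents do not support that without qualification. The candidates come from shared pathways in two layers of one biopsy, so independence is the extreme case. At correlation 0.6 and exit 0.05 the rate is below one half for 16 to 32 candidates.
- A reader might infer that the reported markers would be mostly noise. A simulation in which every marker is null cannot show that, and section 9.4.2 states a prior hypothesis linking failure to collagenase and elastase activity.
- A reader might infer that the plan would advertise good discrimination. It plans no AUC or risk score; the AUC here is only a gauge of optimism.
- Tailoring surgery is mentioned as a theoretical use, not as a stated output of Aim 3.
- The ten-failure rule is not grossly broken on the plan's own terms, since about three null markers would be expected to pass the screen. Counting all candidates is a stricter and sounder standard.
- The 46-failure case assumes the full planned benefit. With no benefit at the 35% control rate there would be 222 × 0.75 × 0.35 = 58.

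**Conclusion.** The concern holds as a range. With no true predictors and 67 failures, about 31% to 95% of trials would keep at least one false predictor. This rests on 16 to 32 candidates, equal correlation between 0 and 0.6 and an exit level of 0.05 to 0.10. Even the lowest figure is too high for a claim of identification, and the missing exit level is a gap in itself. The statement that 67 failures support at least seven variables is also wrong by the plan's own rule: six degrees of freedom are available, one of them for estrogen exposure. This is a secondary aim and nothing here touches the primary outcome. The change is worth making because, as written, the analysis has no means of separating a real marker from a selected one.

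**What to change.** Choose one of two routes in section 9.5:

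1. Fix a short marker list in advance from the pilot, sized so that all candidates plus estrogen exposure fit the expected failures (six degrees of freedom at 67 failures, four at 46).
2. Model all all-site candidates jointly with shrinkage, with estrogen exposure forced in.

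Penalised regression is one sound option and not the only one. Under either route:

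- Repeat any data-driven selection in full inside bootstrap samples.
- Report the number of candidates screened, the selection frequencies and optimism-corrected performance.
- State the exit level if stepwise selection is kept in any form.
- Correct the claim of at least seven variables to six degrees of freedom including estrogen exposure.
- Replace "we will identify important biomarkers that predict greater risk for failure of native tissue repair" with a statement that the analysis will generate candidate biomarkers for failure of native tissue repair.

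The cost is a change of wording, modest analysis time and a more cautious claim. No new data, visits or participants are needed.

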9.2 Sample Size and Randomization

The literature reports failure by the above definition occurring in ~40% of patients with a native tissue USLS (i.e., ~60% “success”).⁶⁹ A 2-sided logrank test with an overall sample size of **188 subjects** (94 each group) achieves 80% power at a 0.05 significance level to detect a hazard ratio of 0.5188 when the proportion of those "surviving" (i.e. "successes") in the control group is **65% compared to 80%** in the treated group, **measured at 1 year**. This presumes the accrual pattern across the study time period (3 years of accrual) is uniform. This N=188 already accounts for **25%** either lost to follow-up *or non-adherent to study cream* in the control and treatment groups. Allowing for an additional **15% loss of participants** from baseline to surgery, **222 total participants** are needed.

Potential problems & alternatives:

Differences in baseline characteristics between the groups may occur by chance, but we will mitigate that risk by stratifying by clinical site, hysterectomy status, and duration since menopause (<10y & ≥10y).

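### Section 9.5 credits 67 failures with at least 7 predictors where its own rule allows 6, and the t-test screen it names has no term for treatment arm

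*Combined protocol and SAP*

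**What the plan says.** Section 9.5 (Aim 3 Outcomes) plans a case-control style analysis of repair failures against successes, to be done "even if CE cream has a null or non-significant effect". Its steps are:

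- Screen: "controlling for CE cream exposure, univariate comparisons will be made of the continuous outcomes from Aim 3". The only test named is the 2-tailed Student's t-test, and the groups are formed from the entire population, both arms together.
- Entry to the joint model: "Those variables that attain a significance level of 0.1 or less in univariate analyses will be considered jointly", in a backward stepwise logistic regression.
- Size of the joint model: a rule of thumb asking for "10 cases of prolapse repair failure) for each predictor added to the model (i.e., for each degree of freedom").
- Capacity claimed under that rule: enough to "analyze up to at least 7 variables in the multivariable model".
- Ground given for the claim: "If a total of 67 cases are identified (i.e., 40% repair failure in 222 participants and 25% patient loss), this would be sufficient to".

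Section 9.2 reports "failure by the above definition occurring in ~40% of patients with a native tissue USLS" from the literature. It powers the trial on success proportions that, "in the control group is 65% compared to 80% in the treated group", imply 35% and 20% failure.

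Three further facts bear on the model's capacity. The biopsy is optional (6.2.3). Protein and enzyme measurements use tissue from the primary site only (9.4.2, Aim 3 Methodology). About 42 such samples, 21 per group, are expected (9.5).

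**The concern.** The stated number of predictors does not follow from the stated rule and the stated number of failures. A minimum of 7 is claimed where the rule gives a maximum of 6.

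The second issue is the screen. CE is expected to move many of these markers; that is the Aim 3 hypothesis. If CE also lowers failure, arm is a common cause of marker level and outcome. A comparison that ignores arm can then select a marker merely because it shows who received CE. The section says its results will identify biomarkers that predict failure and might one day guide the choice of surgery, so a marker that only tracks arm would mislead. What is at stake is the credibility of a secondary, exploratory model, not the trial's main result.

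**Working it through.** **Inputs.** From 9.5: N = 222, 25% loss, 40% failure, 10 failures per degree of freedom, screening level 0.1, about 42 one-site samples. From 9.2: failure 35% (control) and 20% (CE), mean (35 + 20)/2 = 27.5%. Assumed, because the documents give no figure: a CE shift in the marker of 0.5, 1.0 or 1.5 SD.

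**1. The plan's 67.** 222 x 0.75 = 166.5 women; 166.5 x 0.40 = 66.6, about 67. This reproduces.

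**2. The plan's 7.** Terms = failures/10, rounded down. 67/10 = 6.7, so 6. This does not reproduce.
- Seven terms on 67 failures: 67/7 = 9.6 per term. Six terms: 67/6 = 11.2.
- Seven markers plus CE make 8 terms: 67/8 = 8.4 per term.
- Seven terms need 70 failures: 70/166.5 = 42.0% failure at the same loss, or loss of no more than 1 - 70/(222 x 0.40) = 21.2% at 40% failure.
- With CE as one of the 6 terms, 5 remain for markers.

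**3. One-site markers.** 42 x 0.275 = 11.6 and 42 x 0.40 = 16.8, so roughly 12-17 failures. That is 1 term for a model using protein or enzyme data.

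**4. Why the pooled t-test does not control for arm.** It compares the marker mean in failures with that in successes. With equal arms and the 9.2 rates, CE women are 20/(35 + 20) = 36.4% of failures and 80/(65 + 80) = 55.2% of successes. A marker shifted by d SD under CE, with no link to failure within arm, therefore has an expected difference of (0.364 - 0.552) x d = -0.188d SD. With equal failure rates in the arms, CE women are half of each group and the difference is zero.

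**5. Size of the effect on the screen.** Simulation with a normal marker unrelated to failure within arm, failure 35%/20%, thousands of runs per setting. Share passing p <= 0.1 by pooled t-test:

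| Women | 0.5 SD | 1.0 SD | 1.5 SD |
|---|---|---|---|
| 166 | 13-14% | 24-25% | 37% |
| 188 | 15% | 27% | 39% |
| 42 | 12% | 14% | 17% |

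On 166-188 women, a model with marker and arm gives about 9-11% throughout. With no CE effect on failure (35% or 40% in both arms), the t-test itself gives 9.5-10.5%.

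**6. Carry-over to the joint model.** The plan gives no level for staying in the backward selection, so 0.05 and 0.10 were both assumed. After the t-test screen at 35%/20%, null markers are retained in 7-27% (stay level 0.05) or 15-40% (0.10) of runs if arm is left out. If arm is entered but may be removed, the figures are 4-8% or 7-11%. With arm in the screen and kept in the model, they are 4-6% or 9-11%.

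**The case against.** The first part is a rounding slip in a conditional illustration of a rule of thumb: 9.6 failures per term instead of 10. No sample size or decision depends on it. That is fair as to weight. Rounding 6.7 might excuse saying about 7, but not a minimum of 7.

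On the second part, the text does commit to controlling for CE exposure. T-tests within each arm, or the t-test of a coefficient in a model containing arm, would honour that. So the documents do not support the reading that the analysis is bound to be confounded. The narrower point stands: neither method is described, the test as named has no term for arm, and nothing says that CE enters the joint model. The percentages also rest on an assumed marker shift, are much smaller for one-site markers, and vanish if CE does not affect failure. Entering arm in the joint model removes most of the excess.

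A reader might also infer that the 40% failure rate is an error because 9.2 powers the trial on 35% and 20%. The documents do not support that. Section 9.2 itself cites about 40%, and applying it to both arms fits the null-effect case that this part of 9.5 expressly foresees.

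Nor can a general expected number of terms be read off the total sample. Any such range assumes assay data on every retained woman, which an optional biopsy and one-site assays do not provide.

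**Conclusion.** Two corrections are needed, both minor. By the plan's own rule, 67 failures allow 6 degrees of freedom, not 7 or more; this needs no assumption. The screening test as named does not deliver the promised control for CE exposure. The resulting false selection is about 13-39% on 166-188 women, or 12-17% on 42 samples, against a nominal 10%. That holds only if CE lowers failure at the 9.2 rates and shifts the marker by the assumed 0.5-1.5 SD, and it reaches the final model mainly if CE is left out there. Section 9.5 labels Aim 3 descriptive and leaves its p-values unadjusted. The primary comparison and N = 222 are not affected.

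**What to change.** In section 9.5:

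1. Replace the claim of 7 variables with: no more than 6 degrees of freedom at 67 failures, counting CE exposure as one; the actual limit for any model is the observed number of failures with the relevant assay data divided by 10. Add that the biopsy is optional and that protein and enzyme assays come from one site (about 42 samples), so a model using them would carry about 1 term.
2. Replace the pooled t-tests with a marker-failure model, linear or logistic, that includes treatment arm. Keep the 0.1 threshold.
3. State that treatment arm stays in the joint model throughout the backward selection.

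The cost is SAP wording and one change of test, with no new data, visits or participants. The downside is one degree of freedom spent on arm and fewer markers in the joint model. The change is best made before the randomization codes are broken.

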10 DATA COLLECTION AND QUALITY ASSURANCE

10.1 Data Collection Forms

Nurse research coordinators from each clinical site (UTSW, UAB, and WIH) will collect patient data captured by clinic providers and surgeons all blinded to study intervention using case report forms. Specimens (serum, whole blood, cytology specimens for vaginal maturation index, and standardized vaginal wall biopsies in women undergoing vaginal hysterectomy) will be processed by the research coordinators for secure shipment to UTSW, which will serve as the biorepository and site of analysis. Other data will be entered at each site using REDcap®, a Web-based, HIPAA-compliant tool used by many major medical institutions.

A set of electronic case report forms will be developed in REDCap® following the order on existing paper forms. Dropdowns or radio buttons based on allowable responses will be defined where possible. Ranges will be set for numeric values for notification of outliers. Each paper form will provide space for the following identifiers: Site ID, Participant ID (anonymous patient study number), Study Visit Identifier, and Visit Date. The combination of Site / Participant ID will become the unique identifier for each subject in IMPROVE. When a visit packet is complete, the research coordinator will check each paper form for accuracy and completeness. A designated person will enter the data into REDCap®. If any data are missing or questionable, the data entry operator will set the form status to “incomplete.” Once entry is complete, the entry operator will set the form status to “unverified.” A second person will compare the entered data against the paper form. When all are correct, the reviewer will set the form status to “complete.”

Refer to Manual of Procedures (MOP) for a complete inventory of Case Report Forms.

